4.10 Prior and Concomitant Therapy

Patients must have undergone EUS guided drainage procedure using LAMS or sinus tract fistula using plastic stents (pigtailed) in order to enable access to the necrosis. Endoscopic confirmation after completion of

necrosectomy per contrast-enhanced CT will be obtained at 21 (+/-7) days following final DEN procedure. Subjects with walled off pancreatic necrosis are eligible for this study.

4.11 Informed Consent

Prior to the EndoRotor® procedure and enrollment in the ENDOROTOR study, written informed consent will be obtained in accordance with 21 CFR 50.20 and contain the information required by each of the eight basic elements of 21 CFR 50.25(a).

4.12 Inclusion Criteria

Candidates for this study must meet **ALL** of the following Inclusion criteria:

1. Subjects who are ≥ 22 ; inclusive of males and females.
2. Patients with symptomatic pancreatic necrosis due to acute pancreatitis that have an indication to undergo endoscopic necrosectomy after having undergone EUS-guided drainage
3. Imaging suggestive of greater or equal to 30% necrotic material
4. Walled off pancreatic necrosis size ≥ 6 cm and ≤ 22 cm
5. Subject can tolerate repeated endoscopic procedures
6. Subject capable of giving informed consent.
7. Subjects with the ability to understand the requirements of the study, who have provided written informed consent, and who are willing and able to return for the required follow-up assessments through 21 (+/-7) days, as indicated.

4.13 Exclusion Criteria

Subjects will not be included in the study if **ANY** of the following exclusion criteria are met:

1. Subject unable to give informed consent.
2. Subject is unwilling to return for repeated endoscopies.
3. Documented Pseudoaneurysm > 1 cm within the WON
4. Intervening gastric varices or unavoidable blood vessels within the access tract (visible using endoscopy or endoscopic ultrasound).
5. Dual antiplatelet therapy or therapeutic anticoagulation that cannot be withheld for the procedure
6. Any condition that in the opinion of the investigator would create an unsafe clinical situation that would not allow the patient to safely undergo an endoscopic procedure (lack of medical clearance).
7. Pregnant or lactating women or women of childbearing potential who do not employ a reliable method of contraception as judged by the Investigator, and/or are not willing to use reliable contraception for the duration of study participation.
8. Patient is known to be currently enrolled in another investigational trial that could interfere with the endpoint analyses of this trial.

4.14 Study Withdrawal & Lost to Follow Up

Study participation is voluntary and subjects may withdraw their consent at any time. **ALL** enrolled subjects and their status in the study will be included in the study reports.

- **Treated and Study Criteria Not Met:** Subjects who are enrolled and treated, but who are later discovered to not meet all of the study criteria, will remain in the study and complete all of the study testing and follow-up requirements. A protocol deviation will be completed for study subjects who are

found to be ineligible after enrollment. These subjects may be excluded from the Per Protocol analysis depending upon the nature of the protocol deviation.

- **Patient Withdrawal:** Participation in any clinical investigation is voluntary and a patient is allowed to discontinue their participation at any time. Subjects may withdraw at their own discretion with or without reason and without any impact on their continued medical care. If a patient voluntarily withdraws from the study, no additional medical data will be collected, and the patient will not continue in the study.
- Subjects who withdraw from the study will not be replaced; however, if a patient withdraws their consent **BEFORE** being treated with the study device (before insertion of the catheter into the endoscope), and/or before the 21 (+/-7) day follow-up, he or she will not be included in the analysis.
- **Investigator Termination:** The site Investigator may terminate the patient’s procedure if it is in the patient’s best interest not to continue; however, the patient is withdrawn from the study and will not be included in the analysis.
- **Lost-to-Follow-up:** A patient who does not complete follow-up requirements and does not officially withdraw from the study is considered lost-to-follow-up. This does not apply to missed visits where the patient misses one of the follow-up contact time points but completes the subsequent one. In order to consider a patient lost-to-follow-up, site personnel should make all reasonable efforts to locate and communicate with the patient. All attempts to contact the patient must be recorded in the study notes, including the date, time, and name of site personnel who have attempted to contact the patient.

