Clinical Sites:	Up to 6 in the United States and 4 in the EU will enroll subjects.
Enrollment:	The sites will enroll a total of 30 subjects, 15 minimum from the US that meet all inclusion and exclusion criteria.

Inclusion Criteria:	
 1. Subjects who are ≥ 22; inclusive of males and females. 2. Patients with symptomatic pancreatic necrosis due to acute pancreatitis that have an indication to undergo endoscopic necrosectomy after having undergone EUS-guided drainage 3. Imaging suggestive of greater than or equal to 30% necrotic material 4. Walled off pancreatic necrosis size ≥ 6 cm and ≤ 22cm 5. Subject can tolerate repeated endoscopic procedures 6. Subject capable of giving informed consent. 7. Subjects with the ability to understand the requirements of the study, who have provided written informed consent, and who are willing and able to return for the required follow-up assessments through 21 (+/- 7) days, as indicated.
Exclusion Criteria:	
 1. Subject unable to give informed consent. 2. Subject is unwilling to return for repeated endoscopies. 3. Documented Pseudoaneurysm > 1cm within the WOPN 4. Intervening gastric varices or unavoidable blood vessels within the access tract (visible using endoscopy or endoscopic ultrasound). 5. Dual antiplatelet therapy or therapeutic anticoagulation that cannot be withheld for the procedure 6. Any condition that in the opinion of the investigator would create an unsafe clinical situation that would not allow the patient to safely undergo an endoscopic procedure (lack of medical clearance). 7. Pregnant or lactating women or women of childbearing potential who do not employ a reliable method of contraception as judged by the Investigator, and/or are not willing to use reliable contraception for the duration of study participation. 8. Patient is known to be currently enrolled in another investigational trial that could interfere with the endpoint analyses of this trial.
Primary Analysis:	Subjects enrolled in the study and who met all I/E criteria and are treated with the EndoRotor Device.
Study Device:	Interscope EndoRotor® Resection System

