4.5 Clinical Sites & Enrollment

Up to six (6) research sites in the United States and up to four (4) research sites in the European Union will participate in this trial. The sites will enroll a total of 30 subjects meeting all inclusion and exclusion criteria to reach a total of 30 evaluable subjects. Once the informed consent process is completed and final study eligibility has been confirmed, the patient will have the EndoRotor direct endoscopic necrosectomy.

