7.2 Analysis Populations

Study Population: The study population includes all subjects consented at the site. Within this population there are Screened, Safety and Treated populations.

Screened: This population includes all subjects that meet the inclusion and exclusion criteria as specified in the protocol.

Safety: This population includes all subjects in whom the EndoRotor procedure was attempted. Subjects will be analyzed according to the treatment received.

Treated: This population includes all subjects that successfully received the EndoRotor debridement procedure.

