7.3 Sample Size

This study will enroll a total of 30 subjects. Sample size determination is based on the nature and objective of this study and not statistical considerations. The data will be sufficient to provide an assessment of the safety profile of the EndoRotor for DEN in WOPN as well as provide initial efficacy data to support an evaluation of the benefit/risk profile.

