7.4.2 Safety Analysis

All safety data will be displayed and analyzed using descriptive statistical methods. No formal inferential analysis is planned for safety comparisons. The safety endpoint is the absence of any device or procedure related serious significant adverse events (SAEs) within the 21 (+/-7) days following EndoRotor procedure. These will be presented overall and by system organ class and preferred term (PT). This will be conducted on the Safety analysis set overall. Subjects who experience more than one event in a given System Organ Class (SOC) and PT will be counted once within that SOC and PT. The total number of events and the number and percentage of subjects with each event will be reported.

Adverse Events: AEs, SAEs and UADEs will be coded using MedDRA. Treatment Emergent AEs, SAEs and UADEs are defined as events starting or worsening after start of the procedure. The number and percent of patients with Treatment Emergent AEs, SAEs and UADEs will be summarized overall and by primary SOC and preferred term (PT). Subjects who experience more than one event in a given SOC and PT will be counted once within that SOC and PT.

The number and percent of subjects with treatment emergent AEs, UADEs and SAEs will be further presented by severity and by relationship to the device or procedure. In tabulating the severity of AEs on a per subject basis, the greatest severity will be assigned to a subject should there be more than one occurrence of the same AE with different reported severities. Relationship will be categorized as unrelated, possibly, probably and definitely related. The highest level of association will be reported for subjects with different relationships for the same AE.

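### The Protocol Summary and section 7.4.2 name different populations for the primary safety result, so a treated subject later found ineligible is out under one and in under the other

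*Combined protocol and SAP*

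**What the plan says.** Section 4.3 makes freedom from major complications the primary endpoint and treats it as the safety endpoint. Three places bear on who is counted for it.

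- **Protocol Summary, Primary Analysis row:** "Subjects enrolled in the study and who met all I/E criteria and are treated with the EndoRotor Device". Both treatment and full eligibility are required.
- **Sections 7.2 and 7.4.2:** of the safety endpoint, 7.4.2 says "This will be conducted on the Safety analysis set overall". Section 7.2 defines the Safety set thus: "This population includes all subjects in whom the EndoRotor procedure was attempted". Eligibility is not a condition.
- **Section 4.14:** subjects treated and later found ineligible "will remain in the study and complete all of the study testing and follow-up requirements". On analysis it adds: "These subjects may be excluded from the Per Protocol analysis depending upon the nature of the protocol deviation".

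Section 7.2 names Screened, Safety and Treated populations within the Study population of all consented subjects. It has no Per Protocol population, and the term appears nowhere else in the text supplied. On numbers, section 7.3 says "This study will enroll a total of 30 subjects", and section 4.5 speaks of subjects "meeting all inclusion and exclusion criteria to reach a total of 30 evaluable subjects" without defining evaluable.

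**The concern.** The primary endpoint is a safety endpoint, so a reader naturally takes the Summary's Primary Analysis row as the population for it. On that reading the Summary drops any treated subject who failed a criterion, while 7.4.2 keeps that subject. The analyst has two instructions for the same number and no rule of precedence.

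The subjects in dispute may not be a random few. Several exclusion criteria in section 4.13 concern bleeding risk (pseudoaneurysm, varices or vessels in the access tract, antithrombotic treatment), and bleeding is one of the two complications that section 4.3 names. A subject wrongly enrolled against one of these criteria could plausibly be at higher risk of the event being counted. Leaving such subjects out would tend to make the device look safer than it was in the subjects actually treated.

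The trial tests no hypothesis, so the reported complication rate is itself the result. Section 4.7 relies on the data for a regulatory view of benefit and risk, and section 7.1 intends the results to inform the powering of later studies. The denominator of that rate should be unambiguous.

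**Working it through.** **Step 1: the rules side by side**, for a subject treated with the device and afterwards found not to meet a criterion.

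| Place | Rule | Subject counted? |
|---|---|---|
| Protocol Summary, Primary Analysis | treated and met all criteria | No, automatically |
| 7.2 and 7.4.2, Safety set | procedure attempted | Yes, automatically |
| 4.14, Per Protocol analysis | judged by nature of deviation | Undetermined, but no endpoint uses this set |

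The first two rows conflict. They cannot be reconciled by nesting: 7.2 places the Safety set within the consented population, not within the Screened population, which is the only one in 7.2 that requires eligibility. The Summary's set would be the treated part of the Screened population, and 7.2 does not name that combination.

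**Step 2: is there a plan figure to reproduce?** No. Section 7.3 states: "Sample size determination is based on the nature and objective of this study and not statistical considerations". The only usable input is the total of 30. The documents give no expected number of events or of ineligible subjects, so the counts below are assumptions.

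**Step 3: size of the discrepancy.** Assume all 30 are treated and one is later found ineligible. With x events in n subjects, the rate is x/n and the exact (Clopper-Pearson) 95% limits are

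- lower = 0.025 quantile of Beta(x, n − x + 1), or 0 if x = 0;
- upper = 0.975 quantile of Beta(x + 1, n − x).

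For x = 0 the upper limit reduces to 1 − 0.025^(1/n). With n = 29 this is 1 − 0.881 = 0.119.

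If the ineligible subject had an event:

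| Events among 30 | Safety set (7.4.2) | Summary's set | Fall in rate |
|---|---|---|---|
| 1 | 1/30 = 3.3% (0.1 to 17.2%) | 0/29 = 0% (0 to 11.9%) | 3.3 points |
| 2 | 2/30 = 6.7% (0.8 to 22.1%) | 1/29 = 3.4% (0.1 to 17.8%) | 3.2 points |
| 3 | 3/30 = 10.0% (2.1 to 26.5%) | 2/29 = 6.9% (0.8 to 22.8%) | 3.1 points |

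In the first row, freedom from complications goes from 96.7% to 100%.

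If the ineligible subject had no event and one other subject did, the change is from 1/30 = 3.3% to 1/29 = 3.4%, which is negligible. The conflict matters only when an ineligible subject has an event.

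**The case against.** The strongest reply is that section 7 is the operative statistical text. It assigns the safety endpoint to everyone attempted, and the Summary row is a one-line entry that does not say which endpoint it governs. Section 4.14 requires every enrolled subject's status to be reported, keeps these subjects in follow-up and requires a deviation form. Section 10.2 sends serious adverse events and safety endpoint events to an independent committee whose reports cover ineligibility and protocol violations. Section 7.1 sets no success criterion and 7.4.2 plans no inferential safety comparison, so no decision could flip. The intervals in the illustration also overlap heavily.

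Most of this stands, and it limits the consequence. It does not remove the contradiction: the Summary uses the words Primary Analysis, the primary endpoint is safety, and no precedence is stated.

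A reader might go further and infer that the Per Protocol sentence in 4.14 lets a harmed subject be taken out of the safety result after the fact. The documents do not support that. The discretion reaches only a Per Protocol analysis that 7.2 does not define and to which no endpoint is assigned. The exclusion that could change the primary figure is the Summary's, and that one is automatic, not case by case.

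A reader might also infer that ineligibility would be looked for once a complication had occurred. That is possible in an open-label trial, but no passage shows it. Section 5.3.1 requires eligibility to be confirmed and recorded before the index procedure, and section 8.6.3 requires notice of serious deviations, including those on eligibility, within five working days of awareness. These provisions reduce the opportunity without closing it.

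**Conclusion.** Wrong as written: the primary analysis set is contradictory. Under the Summary a treated but ineligible subject is out of the primary result; under 7.2 and 7.4.2 the same subject is in.

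The size depends on assumed counts. One ineligible subject with an event moves the rate by about 3 percentage points out of 30 subjects, and if it is the only event the primary figure falls from 3.3% to zero. This assumes that all 30 are treated, that exactly one is later found ineligible, and that the safety endpoint in 7.4.2 is the analysis of the primary endpoint in 4.3.

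The event would not vanish from the report, because the Safety-set tables and the accounting of all enrolled subjects would still show it. What is at risk is the figure presented as primary.

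The undefined Per Protocol analysis in 4.14 is a separate, smaller defect. It leaves an exclusion with no list of deviations, no decision-maker and no timing, attached to a set that has no use.

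**What to change.** 1. **Protocol Summary, Primary Analysis row:** state that the primary safety endpoint is analysed in the Safety population of 7.2, including treated subjects later found ineligible.
2. **Section 4.14:** say the same in the bullet on subjects treated without meeting the criteria.
3. **Per Protocol sentence in 4.14:** delete it. If the set is wanted, define it in 7.2 by a list of eligibility deviations fixed in the protocol and judged on baseline data without reference to outcome, and use it only as a sensitivity analysis of effectiveness. Requiring the decision before database lock would not be enough, because outcomes in an open-label trial are known well before lock.

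The cost is wording in two places, or three if a Per Protocol set is kept. No extra subjects, visits or data are needed.

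The bullets in 4.14 on withdrawal and investigator termination also take subjects out of the analysis. They are a separate matter and this point does not rest on them, but whoever edits 4.14 should check them against the new sentence.

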4.3 Primary Endpoint

The primary endpoint of this study is the freedom from major complications. The safety endpoint will include an assessment of the safety of the EndoRotor when performing endoscopic necrosectomy. For the purpose of this study, the safety evaluation shall include complications associated with endoscopic necrosectomy through the 21 (+/-7) day follow-up period. Potential endoscopic complications include perforation and bleeding.

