4.9 Subject Screening

Following placement of stent and determination of need for necrosectomy study eligibility is confirmed and the patient will receive the EndoRotor® intervention. The patient will be enrolled upon insertion of the catheter into the endoscope. Screening shall include:

- Pregnancy test – within 1 day of the procedure.
- Medical clearance in advance of the procedure.
- WOPN resulting from necrotizing pancreatitis per high resolution vascular CT with the characteristics per the 2012 Revised Atlanta Classification.
- Imaging suggestive of greater than 30% necrotic material
- WOPN size ≥ 6 cm and ≤ 22 cm

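### Section 4.14 removes subjects whose procedure the investigator stops from an unnamed analysis, in conflict with the Safety set of Sections 7.2 and 7.4.2

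*Combined protocol and SAP*

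**What the plan says.** Section 4.14 has three rules that bear on who is analysed.

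- Investigator termination, where stopping the procedure is judged best for the patient: "however, the patient is withdrawn from the study and will not be included in the analysis".
- Withdrawal of consent. The clause begins with withdrawal before the device is used and continues: "and/or before the 21 (+/-7) day follow-up, he or she will not be included in the analysis".
- Subjects treated but later found ineligible stay in the study and complete follow-up: "These subjects may be excluded from the Per Protocol analysis depending upon the nature of the protocol deviation".

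Section 7.2 defines Screened, Safety and Treated populations but no per-protocol set. Of the Safety population it says: "This population includes all subjects in whom the EndoRotor procedure was attempted". Section 7.4.2 defines the safety endpoint as the absence of device- or procedure-related SAEs in the 21 (+/-7) day window and adds: "This will be conducted on the Safety analysis set overall".

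The Primary Analysis line of the Protocol Summary gives a different group: "Subjects enrolled in the study and who met all I/E criteria and are treated with the EndoRotor Device".

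Section 4.3 states: "The primary endpoint of this study is the freedom from major complications". Sections 7.1 and 7.4.2 make clear that the endpoints do not define study success and that safety is described without formal inference.

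**The concern.** A procedure that was begun and then stopped was attempted. Under 7.2 and 7.4.2 that subject counts in the safety endpoint; under 4.14, read as written, the subject does not. The Protocol Summary would also drop treated subjects who turn out to be ineligible, whom 4.14 keeps in the study and allows to be left out only of a per-protocol analysis.

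This matters because stopping a procedure in the patient's interest may be linked to the outcome being measured. In a single-arm study of 30 subjects, the reported safety percentage is a principal result, and Sections 4.7 and 7.3 intend it to support the benefit/risk profile. The study is also open label, so an unsettled set could be chosen after outcomes are known.

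**Working it through.** **Step 1. Compare the rules for subjects exposed to the device.**

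| Subject | 7.2 / 7.4.2 Safety set | Section 4.14 | Protocol Summary, Primary Analysis |
|---|---|---|---|
| Procedure started, then stopped by investigator | In | Out of an unnamed analysis | In if eligible and counted as treated |
| Treated, consent withdrawn before the 21-day visit | In | Out or not addressed, depending on how and/or is read | In if eligible |
| Treated, later found ineligible | In | In the study; may leave a per-protocol analysis | Out |

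The first row is the clear conflict. The second depends on the reading. The third is a conflict between the Protocol Summary and the other two places. Withdrawal before any attempt creates no conflict, and neither does a stop before any attempt.

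**Step 2. Look for text that settles it.** No section gives precedence. Section 4.14 says that the status of all enrolled subjects will be reported, but that does not place them in an analysis set. Section 7.5 limits analyses to available data without saying whether a subject with observed events stays in. Section 5.3.3 ties follow-up and analysis to the catheter, but its sentence lacks a verb.

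The enrolment point does not settle it either. Section 4.9 says "The patient will be enrolled upon insertion of the catheter into the endoscope", while 5.3.3 speaks of enrolled subjects who are not treated, and 5.3.4 and Appendix 1 put the index procedure within 2 weeks of enrolment.

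**Step 3. Narrow the affected group.** Appendix 2 says that bleeding at the index procedure needing intervention during that procedure is not an SAE. A stop for that reason would therefore not count as an event under 7.4.2 on either set. Under 10.2, a related perforation, pancreatic leak or procedural bleed that cannot be managed endoscopically suspends the study, so such an event would be seen whatever set is used. What remains is related SAEs between these two, for example a perforation managed endoscopically.

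**Step 4. Illustrate the size.** The plan has no figure to reproduce: Section 7.3 says that N = 30 is not statistically derived, and no stopping, withdrawal or SAE rate is given. The only in-document anchor for this use is the series in Section 1.2 (12 patients, 23 procedures, no perforation or bleeding), which is not an SAE rate. All event and removal counts below are therefore assumed.

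Rate = x/n. Exact (Clopper-Pearson) 95% limits: lower = the 2.5% point of Beta(x, n − x + 1), or 0 if x = 0; upper = the 97.5% point of Beta(x + 1, n − x). For x = 0 the upper limit is 1 − 0.025^(1/n).

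| Safety set (7.2) | Removed under 4.14 | Result under 4.14 | Change in rate |
|---|---|---|---|
| 0/30 = 0% (0 to 11.6%) | 2 event-free | 0/28 = 0% (0 to 12.3%) | 0 |
| 1/30 = 3.3% (0.1 to 17.2%) | 1 with event | 0/29 = 0% (0 to 11.9%) | −3.3 points |
| 3/30 = 10.0% (2.1 to 26.5%) | 1 with event | 2/29 = 6.9% (0.8 to 22.8%) | −3.1 points |
| 3/30 = 10.0% (2.1 to 26.5%) | 2 with event | 1/28 = 3.6% (0.1 to 18.3%) | −6.4 points |
| 3/30 = 10.0% (2.1 to 26.5%) | 1 event-free | 3/29 = 10.3% (2.2 to 27.4%) | +0.3 points |

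Each row is a separate hypothetical dataset. Removing event subjects lowers the rate; removing event-free subjects leaves it unchanged or raises it slightly.

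**The case against.** The strongest reply is that the statistical section already names the set. Section 7.4.2 assigns the safety endpoint to the Safety set and 7.2 defines it, whereas 4.14 is a withdrawal section that never mentions safety. A statistician working from Section 7 would keep these subjects. That is a fair account of the likely outcome, and nothing shows that 4.14 would govern the safety table. But the termination rule is unqualified, although the same section names a per-protocol analysis when it wants one. The reply therefore lowers the severity without removing the conflict.

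The reply on consent withdrawal is stronger. Read as requiring both conditions, the clause covers only untreated subjects and there is no conflict. Read as either condition, it would suit an effectiveness analysis, because clearance cannot be assessed without the 21-day CT. A reader might infer that treated subjects who withdraw are plainly excluded from the safety results; the wording is too ambiguous to support that.

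It is also fair to say that all enrolled subjects' status is reported and that an independent committee reviews serious adverse events (Section 10.2). Neither fixes the numerator or denominator of the safety endpoint.

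**Conclusion.** The plan contradicts itself on whether a subject whose procedure was started and then stopped counts in the safety endpoint, and the Protocol Summary adds a third set. That rests on the text alone and is firm. The consent-withdrawal half holds on only one reading of an ambiguous clause.

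A reader might go further and infer that 4.14 biases the safety result in the device's favour. The documents do not support that. They give no reasons for or frequency of stopping, intra-procedure bleeding at the index procedure that needs intervention is not counted as an SAE, and the gravest related events suspend the study. The direction and size of any bias are uncertain. In the illustrations one removed subject moves the rate by between −3.3 and +0.3 points, with intervals that overlap widely.

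Because safety is descriptive and there is no success threshold, this should be fixed, but it does not invalidate the design.

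**What to change.** - In 4.14, state that every subject in the 7.2 Safety set (procedure attempted) stays in the safety endpoint analysis, with data up to consent withdrawal or last contact. Tie this to the attempt, since the documents disagree on when enrolment occurs.
- Confine the 4.14 exclusions and the eligibility restriction in the Protocol Summary to a named effectiveness or per-protocol set, and define that set in 7.2.
- Resolve the and/or in the consent-withdrawal clause.
- Reconcile 4.14, which withdraws stopped subjects from the study, with Section 10.5, which has adverse events followed until resolved or stable, so that safety data are not lost for subjects who still consent.
- Report the numbers stopped and withdrawn, with reasons and length of follow-up.

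The cost is minor wording work in 4.14, 7.2 and the Protocol Summary, and a reported event rate that may be less favourable.

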5.4.2 Follow-up Visit 21 Days (± 7 days)

All subjects will return to the clinic for the 21 (+/-7) day visit as determined from the last EndoRotor procedure. Results of the following study procedures will be recorded in the subject's source medical record and on the appropriate CRF:

- CT Scan Imaging: Record results and the percent resolution of necrotic debris in the collection being treated
- Surveillance endoscopy (only if clinically required) whereby physician can use local standard of care to continue to treat the patient if required
- Physical Exam
- SF-36 Questionnaire

All subjects will exit from the study after this visit; however, all subjects should be followed according to the Investigator's clinical standard practice guidelines for safety.

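### Section 4.14 drops investigator-terminated subjects from the analysis even after device exposure, against the Safety population in 7.2 and 7.4.2, and leaves their day-21 follow-up unclear

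*Combined protocol and SAP*

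**What the plan says.** The Investigator Termination bullet of 4.14 allows the site investigator to stop a procedure when continuing is not in the patient's interest, and then adds: "however, the patient is withdrawn from the study and will not be included in the analysis". It does not separate stops before device exposure from stops after it, and it does not name an analysis set.

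Other sections place the same subject inside the study:

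- 4.9 fixes the moment of enrollment: "The patient will be enrolled upon insertion of the catheter into the endoscope".
- 7.2 defines the Safety population: "This population includes all subjects in whom the EndoRotor procedure was attempted". It has a separate, narrower Treated population: "This population includes all subjects that successfully received the EndoRotor debridement procedure".
- 7.4.2 says of the safety endpoint: "This will be conducted on the Safety analysis set overall".
- 4.3 sets the scope of the primary safety evaluation: "complications associated with endoscopic necrosectomy through the 21 (+/-7) day follow-up period".

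On follow-up, 5.4.2 states "All subjects will return to the clinic for the 21 (+/-7) day visit as determined from the last EndoRotor procedure" and "All subjects will exit from the study after this visit". Section 10.5 monitors adverse events from enrollment to study exit and follows known events until they resolve or stabilise. The termination bullet itself says nothing about follow-up.

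**The concern.** A best-interest stop is not a random reason for leaving a study. The complications named in 4.3, perforation and bleeding, are obvious reasons to end a session. A rule that removes stopped subjects can therefore remove endpoint events because they occurred. The loss does not depend on missing data: a perforation already recorded leaves the result together with its subject. Because 4.2 allows up to four EndoRotor procedures, a stop at a later session would also take out whatever happened at the earlier ones.

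The follow-up question comes on top of this. If withdrawn means that study visits end, complications that first appear after discharge may go unrecorded in the subjects who plausibly have the highest risk.

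At stake is the credibility of the freedom-from-major-complications rate. The study is primarily a safety evaluation (4.7), has no comparator and no formal safety test, and its data are meant to support the benefit-risk profile (4.7, 7.3). That rate is the main safety result.

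**Working it through.** **There is no plan figure to reproduce.** The sample size of 30 is stated not to rest on statistical considerations (7.3), and no performance goal or margin is given. The check is a comparison of the text, followed by an illustration.

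**Step 1: set membership.** Take a subject whose catheter is inserted and whose procedure is then stopped.

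| Section | Consequence for this subject |
|---|---|
| 4.9 | Enrolled |
| 7.2, Safety | In: the procedure was attempted |
| 7.2, Treated | May be out: not successfully received |
| 7.4.2 | Counted: the safety endpoint uses the Safety set |
| 4.14, Investigator Termination | Withdrawn and out of the analysis |

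The last row contradicts rows two and four, and no section says which prevails. Effectiveness does not need the exclusion, because the Treated set already serves that purpose.

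**Step 2: follow-up.** Two readings are open.

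- *It continues.* 5.4.2 covers all subjects and places study exit after the day-21 visit; 10.5 monitors adverse events to exit. The Patient Withdrawal bullet of 4.14 expressly ends data collection, and the termination bullet has no such sentence.
- *It ends.* The subject is withdrawn from the study. By contrast, another bullet of 4.14 expressly keeps treated but ineligible subjects in the study with full follow-up.

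On the second reading, known events are still followed (10.5) and Appendix 1 has an adverse event assessment at discharge. What may be lost is new events after that. The visit falls 21 − 7 = 14 to 21 + 7 = 28 days after the last procedure, which is an upper bound on the unobserved window.

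**Step 3: size (illustration).** The documents give no stop rate and no event rate among stopped subjects. Assume 30 subjects, 3 with an event, so the true complication-free rate is 27/30 = 90.0% (exact Clopper-Pearson 95% CI 73.5 to 97.9%). Let k subjects be stopped, e of them with an event. After exclusion:

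rate = (30 − k − (3 − e)) / (30 − k)

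| k | e | Rate after exclusion | Shift, points |
|---|---|---|---|
| 1 | 1 | 27/29 = 93.1% | +3.1 |
| 2 | 2 | 27/28 = 96.4% | +6.4 |
| 3 | 3 | 27/27 = 100% | +10.0 |
| 2 | 1 | 26/28 = 92.9% | +2.9 |
| 1 | 0 | 26/29 = 89.7% | −0.3 |
| 2 | 0 | 25/28 = 89.3% | −0.7 |
| 3 | 0 | 24/27 = 88.9% | −1.1 |

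If the subject is kept in the set but one event goes unobserved, the rate is 28/30 = 93.3% (+3.3).

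The effect on the event rate is plainest when every event occurs in a stopped subject. With k = e = 1, and that the only event in the study, 1/30 = 3.3% (95% CI 0.1 to 17.2%) becomes 0/29 = 0% (0 to 11.9%). With k = e = 3, 3/30 = 10.0% (2.1 to 26.5%) becomes 0/27 = 0% (0 to 12.8%).

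**The case against.** The best defence is that 4.14 does not name a set, whereas Section 7 does. A statistician could follow 7.2 and 7.4.2 and read the exclusion as limited to effectiveness or per-protocol work. That reading is possible but weak: 4.14 names the Per Protocol analysis elsewhere when it means that, and this bullet is unqualified. Nor can it be limited to stops before exposure, since the preceding bullet spells out catheter insertion when it wants that distinction. The synopsis adds a third description of the primary analysis (enrolled, eligible and treated with the device), which does not settle the matter.

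On follow-up, the contrary text is real. Besides the points in Step 2, 5.3.3, although its sentence is incomplete, points towards following and analysing catheter-exposed subjects. This half therefore stands only as an ambiguity that sites could resolve differently.

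Serious events would not go unseen. SAEs are reported within 24 hours (8.6.1, 10.5), the DMC reviews SAEs and safety endpoint events, and a related perforation, leak or bleed that cannot be managed endoscopically suspends the study (10.2). DMC reports also cover early discontinuation, and 4.14 reports every enrolled subject's status. These measures protect patients and oversight, but none of them returns the subject to the safety rate.

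The size is assumed, and the larger shifts require every stopped subject to have an event. Appendix 2 does not treat index-procedure bleeding managed during the procedure as an SAE, so some stops would not count under the SAE-based endpoint of 7.4.2. A one-subject shift is also small beside the confidence interval. All of this stands and limits the consequence. It does not justify the rule.

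**Conclusion.** The concern holds. As written, 4.14 is a wrong rule rather than a missing detail: it excludes exposed subjects from the safety result for a reason that can be the outcome, and it contradicts the Safety set that the plan itself defines. On follow-up the finding is narrower: the text allows two readings and should allow one.

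From an assumed 27/30, the shift ranges from −1.1 to +10.0 points for one to three stopped subjects. The direction is upward only if stopped subjects have more events than the others, which is plausible but not documented. The practical consequence is limited because the endpoint is descriptive (7.4.2) and, under 7.1, does not define study success. It should be fixed, with medium confidence in how much it would matter in practice.

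**What to change.** Replace the Investigator Termination bullet of 4.14 with wording to this effect:

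*Stopping a session, or EndoRotor treatment altogether, after catheter insertion is not withdrawal from the study. The subject remains in the Safety population and completes adverse event monitoring and the day-21 (+/-7) visit with CT, counted from the last EndoRotor procedure, unless consent is withdrawn. A subject whose procedure was not successfully received may be omitted from the Treated population only.*

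The cost is one reworded bullet, processed as a protocol amendment with IRB and, as appropriate, FDA review (8.1, 9.9); a few more day-21 visits and CTs of a kind already in Appendix 1; and possibly a less favourable safety rate. No new analysis set is needed. The Patient Withdrawal provisions of 4.14, which also exclude subjects who withdraw consent before the day-21 visit, raise a related but separate question that this change does not settle.
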